Protocol Number: 18-DA-N095

Title: **Just-In-Time Adaptive Interventions for Addictive Behaviors (JITAI)**

Date of this submission: December 18, 2019 / Version 2.2

NIH Principal Investigator:

[name].
Branch: CPTR
Institute: NIDA IRP
[name]
[name]
[name]
[contact]
email: [contact]

A. Précis

Background. Our research group has made extensive use of ecological momentary assessment (EMA) to understand people's daily experiences with opioid craving, use, and lapse. We have also administered clinic-based psychotherapies such as cognitive-behavioral therapy (CBT), in which clients learn to avoid, escape, resolve, or reframe problems (such as stress) that can trigger lapses to drug use. CBT contrasts with ACT (Acceptance and Commitment Therapy), a mindfulness-based approach in which difficult thoughts and feelings are viewed as necessary and potentially valuable components of a full life, to be experienced observantly rather than resolved or reframed. CBT and ACT can and do coexist in a single treatment plan, but we know of no systematic attempt to reconcile their differences. We have also not tried to administer either of them on a mobile device.

Objective. To test a just-in-time adaptive intervention (JITAI)—a treatment given when and where it is needed. Our JITAI will be delivered via smartphone app and will combine elements of two widely used treatments for addiction: CBT and ACT. Our goal is *not* to bring another branded app onto the market, but rather to clarify when and for whom the generic components of such apps are effective or not. This will include determining when CBT is more helpful than ACT and vice versa.

Participant population. Outpatient adults who are in treatment for opioid use disorder (OUD)—up to 185 enrolled (35 for a formative-interview phase, 150 for a trial) for a target of 115 evaluable (30 interviewees, 85 trial participants). Target enrollment will include 40% women and 60% minorities (mostly African-American). In the trial, some participants will receive buprenorphine in our clinic, and others will be receiving buprenorphine or methadone elsewhere; this is a procedural matter, not a component of the experimental design.

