Experimental design. After a formative-interview phase, the study will be run as a microrandomized trial that will also include a conventionally randomized between-groups clinical-trial component. In microrandomization, interventions are randomized at the momentary level within person; the effect is measured proximally (e.g., 20 minutes later). This is a powerful way to assess the effects of different interventions administered in the field and to examine “strategy-situation fit,” i.e., whether interventions are differentially effective under specific momentary circumstances. We are powering our study mostly to detect (1) any effect of CBT or ACT versus control moments with no intervention given, and (2) preferential advantages of CBT over ACT, and vice versa, as a function of the participant’s ability to control (change, escape) a given situation. The between-groups aspect of the design (JITAI group versus EMA-only control group) is needed to demonstrate an effect of our JITAI on traditional, distal measures of outcome, such as reductions in opioid use.

Methods. In the formative-interview phase, we will conduct interviews with people in treatment for OUD who express interest in using a mobile treatment app. We will ask them about day-to-day challenges they currently face in maintaining progress toward their treatment goals, and ask them what might be helpful. Then we will show them item lists, onscreen mockups, and/or functional demos, and we will ask interviewees to comment on the app’s likely usefulness, its likely pitfalls, and how we could improve it.

In the clinical trial, participants will be randomized to one of two groups (JITAI vs. EMA-only control). During weeks 1-2, all participants will have baseline assessments of coping styles and personality, and all JITAI participants will be shown a video introducing basic concepts of CBT and ACT. For weeks 3-10 (8 weeks), participants will carry smartphones for EMA with or without JITAI. During week 11, participants will be readministered some of the

assessments from baseline. Participants receiving buprenorphine from us will then be offered a dose taper or encouraged to transfer to continued treatment elsewhere. All participants will come to our clinic thrice weekly for urine testing throughout participation.

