2. *Strategy-situation fit.* The effects of the messages will be moderated by the circumstances in which they are provided (Haines et al., 2016). For example:

- In situations that are under the participant's control, greater proximal benefits will be associated with active CBT strategies such as avoidance or direct action.
- In situations that are largely out of the participant's control, greater proximal benefits will be associated with acceptance (ACT). Some CBT strategies, such as distraction or cognitive reappraisal of the situation (i.e., interpreting a seemingly negative event as a positive event) might also be useful in those situations, but there is evidence that accepting one's own negative thoughts and emotions (an ACT strategy) confers unique benefits beyond those of reappraisal, shortening the duration of negative mental experiences (Ford et al., 2017).

Hypotheses for *distal* effects of intervention (time scale of weeks):

3. *Main effect of intervention.* The group randomized to JITAI will have better outcomes (e.g. less drug use, higher self-efficacy, a greater increase in flexibility of coping styles) than the EMA-only control group when assessed at week 11.
4. *Differential responses over time.* This “distal” effect is really a summary of proximal effects. We and others have found that drug abstinence is delayed after initiation of CBT, as skills become practiced and integrated into daily life (Carroll et al., 1994; Epstein et al., 2003). We hypothesize, however, that CBT messages will be rated as helpful almost immediately, due to their pragmatic, straightforward nature. ACT messages, which are usually more oblique and koanlike, may have to be seen several times, or lived with for several weeks, before being rated as helpful—but may also stand up better to repetition.
5. *Trait predictors of responsiveness.* Like responsiveness over time, this “distal” effect is really a summary of proximal effects. Although we are not powering the study to assess treatment matching at the person level, we will examine whether trait variables such as personality and preferred coping styles are associated with differential responsiveness to CBT-based versus ACT-based messages.

Push versus pull:

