2. Analysis of study outcomes

Hypothesis 1, proximal: Main effect of messaging (delivery of either a CBT-based or ACT-based message will increase self-efficacy and decrease cravings and other negative states 20 minutes later, compared with the control message).

We will use multilevel random-intercept models (with data from the JITAI group only) to test the hypothesis of a proximal benefit of messages. The dependent variables, in separate models, will be participants' ratings of self-efficacy, craving, mood, and message helpfulness in EMA "post" assessments, controlling for the ratings in "pre" assessments. The main independent variable will be message type: active (CBT or ACT) versus none ("thank you" control condition). We will use an autoregressive error structure to account for within-person correlations. A significant beneficial effect on any of the outcome measures (self-efficacy, craving, mood, message helpfulness) will be taken as partial support for the hypothesis; significant beneficial effects on all the outcome measures will be taken as full support.

Hypothesis 2, proximal: Strategy-situation fit (the effects of the messages will be moderated by the circumstances in which they are provided).

The main analysis here (again, with data from the JITAI group only) will be a test of whether CBT messages are most effective in controllable situations and ACT messages are most effective in noncontrollable situations. We will categorize a situation as *noncontrollable* when a participant gives a response of less than 50/100 on either of these two "pre" items: (1) "I could easily be somewhere else right now if I wanted," (2) "I could easily get out of what I'm doing right now." Otherwise, we will categorize the situation as *controllable*. In the subset of instances in which an active message was given, multilevel models similar to those for hypothesis 1 will be run with the predictors Intervention Type (either CBT or ACT), controllability (y/n), and their interaction. A significant interaction (in the expected direction) on any of the outcome measures (self-efficacy, craving, mood, message helpfulness) will be taken as partial support for the hypothesis; significant beneficial effects on all the outcome measures will be taken as full support.

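### The support rule for hypothesis 2 rests on an interaction, which shows moderation but not that CBT or ACT is the better message in its own situation

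*Combined protocol and SAP*

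**What the plan says.** The aim is stated as a comparison of the two messages. Section A (Précis, Objective) speaks of "determining when CBT is more helpful than ACT and vice versa". The Experimental design paragraph of the Précis says that the study is powered mainly for two effects, one of which is "preferential advantages of CBT over ACT, and vice versa", as a function of the participant's ability to control the situation. Section D, hypothesis 2, is headed as moderation by circumstances. It then gives as examples a CBT advantage in controllable situations and an ACT advantage in uncontrollable ones, while allowing that some CBT strategies may help in the latter too.

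Section I.2 sets out the main analysis for hypothesis 2 as "a test of whether CBT messages are most effective in controllable situations and ACT messages are most effective in noncontrollable situations". The data are restricted: "In the subset of instances in which an active message was given". In those moments, "multilevel models similar to those for hypothesis 1 will be run with the predictors Intervention Type (either CBT or ACT), controllability (y/n), and their interaction".

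The decision rule has two grades. Partial support is earned by "A significant interaction (in the expected direction) on any of the outcome measures" (self-efficacy, craving, mood, message helpfulness). Full support asks for significant benefit on all four, but does not say which contrast must show it. Section I.3 sets two-tailed significance at .05. Section J states power .90 for a strategy-situation fit of d = .16 with 49 evaluable JITAI participants and a 50-50 split between controllable and uncontrollable situations.

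**The concern.** The question is which message is better within each situation. The rule looks only at a difference of differences: the CBT-ACT gap in controllable moments minus the gap in noncontrollable moments. The expected direction fixes the sign of that one quantity. The same sign arises when CBT leads by a lot in controllable moments and by a little in noncontrollable ones, so that ACT is better nowhere. Section D's allowance for CBT strategies in uncontrollable situations makes that pattern plausible.

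If full support is read as four significant interactions, it has the same gap, since four interactions do not establish a crossover any more than one does. Because the thank-you moments are left out of this model, the analysis also does not show whether the favored message beats no message in that situation.

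Hypothesis 2 is listed among the primary outcomes in the Précis, and it set the JITAI sample size in section J. A finding of fit that cannot be told apart from a general CBT advantage would not answer the question the trial asks.

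**Working it through.** **1. The plan's own figure.** Section J's result for hypothesis 1 (25 participants) is reproduced by the microrandomized-trial F-test formula: a quadratic effect with 3 parameters, 3 baseline parameters, df (3, N - 6), and noncentrality N × Σ[availability × ρ(1 - ρ) × effect²]. With the stated inputs, power is .897 at N = 24 and .913 at N = 25.

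For hypothesis 2 the reduced availability is not given. Assuming an average of .20 (one third of .60), ρ equal to the controllable share, and an effect starting at .05, the detectable d at N = 49 and power .90 is .1604, .1636 and .1744 for splits of 50-50, 60-40 and 70-30. The stated values are .16, .164 and .174. The match depends on treating controllability as if it were the randomized factor. That is not a CBT-versus-ACT contrast within a situation, so section J does not fix the standard errors needed here. Two values are used below as a range.

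**2. Standard errors** (assumed throughout: normal approximation, 50-50 split, equal cells).

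- Back-calculated from the stated power, treating d = .16 as the interaction: SE(interaction) = .16 / (1.960 + 1.282) = .0494, and SE(contrast within a situation) = .0494 / √2 = .0349.
- Built from section J's counts, with unit SD and independent errors assumed: 56 × 4 = 224 moments per person; 49 × 224 × .60 available × 2/3 active = 4,390 active moments; 4,390 / 4 = 1,098 per cell. SE(contrast) = √(2 / 1,098) = .0427, and SE(interaction) = .0427 × √2 = .0604.

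**3. Probability that the current rule is met on one outcome, with a true interaction of .16.**

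- Smaller SE: Φ(.16/.0494 - 1.960) = .90.
- Larger SE: Φ(.16/.0604 - 1.960) = .755, about .75.

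This depends only on the interaction, so it is the same for every pattern whose two contrasts differ by .16.

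**4. What lies behind the interaction.** Differences are CBT minus ACT, scored so that positive favors CBT, in controllable / noncontrollable moments. The rows were simulated with 2 million draws each. Each pair gives the result at the smaller, then the larger SE.

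| True differences | Current rule met | Interaction plus opposite, predicted signs | ACT significantly better when noncontrollable | Both contrasts significant, as predicted |
|---|---|---|---|---|
| +.08 / -.08 (crossover) | .90, .755 | .895, .75 | .63, .47 | .40, .22 |
| .16 / 0 | .90, .755 | .495, .47 | .025, .025 | .025, .024 |
| .20 / .04 (CBT better in both) | .90, .755 | .13, .17 | .001, .002 | .001, .002 |

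Check by hand: each .08 contrast has power Φ(.08/.0349 - 1.960) = .63 or Φ(.08/.0427 - 1.960) = .47. The two contrasts use separate moments, so joint power is .63² = .40 or .466² = .22.

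The current rule is met equally often in all three rows. Adding the sign condition costs almost nothing under the crossover and removes most of the false credit in the last row.

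**The case against.** Five points can be made for the plan.

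- **Grading.** One significant interaction is called partial support, not confirmation. That stands: a reader might infer that the plan declares hypothesis 2 established by a single interaction, and it does not. The grade, however, counts outcomes. It does not ask which message is better in a situation.
- **Moderation.** The general statement of hypothesis 2 is moderation, for which an interaction is the standard test, and the directional patterns in section D are introduced as examples. That stands for the general statement. Section I.2, however, names the directional claim as what the main analysis tests, and the Précis refers to advantages both ways. One could read most effective as where each message works best, but the Précis wording makes the CBT-versus-ACT reading the natural one.
- **Estimability.** The model includes message type and controllability, so both within-situation differences follow from its coefficients and a general CBT advantage would be visible. That stands. The gap is in pre-specification and in the wording of support.
- **Consequences.** A reader might infer that the plan would go on to switch messages by situation. The documents contain no such rule for choosing messages in a later app, so that inference is not supported.
- **Cost of strictness.** If support required both intervals to exclude zero, joint power of .90 would need about 49 × [(1.960 + 1.632) × .0349/.08]² = 121 JITAI participants, or about 180 with SE .0427, against 50 planned. That stands, and it is why the strict condition is proposed as a separate tier and not as the threshold for support.

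Limiting the model to active messages does fit a CBT-versus-ACT question. Hypothesis 1 compares active messages with control, though pooled over situations.

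**Conclusion.** The point holds as a mismatch between the claim and the rule. A significant interaction in the expected direction shows that controllability moderates the CBT-ACT difference; it does not show that either message is the better one in its own situation, and no contrast that would show this is pre-specified. That conclusion is logical and does not depend on any standard error.

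Its size does depend on assumptions. With a true interaction of .16, the rule is met on one outcome with probability about .75 to .90, and equally so under a crossover and when CBT is better in both situations. The upper value takes the stated .90 power at d = .16 to refer to the interaction. The lower takes section J's counts with unit SD and independent errors. Because section J gives neither the reduced availability nor the contrast behind d = .16, neither value should be read as implied by the plan.

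**What to change.** Amend section I.2, hypothesis 2, before analysis.

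1. From the planned active-message model, pre-specify and report CBT minus ACT with a 95% CI in controllable and in noncontrollable moments, for each outcome.
2. Tier the wording:
   - (a) a significant interaction only: moderation;
   - (b) a significant interaction plus within-situation estimates of opposite, predicted signs: support for strategy-situation fit;
   - (c) both CIs also excluding zero: a demonstrated crossover.
3. Apply the same tiers to partial and full support, and name the contrast that full support requires on all four outcomes.
4. For self-efficacy, craving and mood only, add a supporting model on all moments that compares each message with the thank-you control within situation. Helpfulness cannot be included, because section E.3 collects that rating only after a CBT or ACT message.

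Tier (b) is not proof that ACT beats CBT. When the true difference in noncontrollable moments is zero (.16/0), it is still reached about half the time, so the CIs must be shown with it.

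The cost is a little more analysis and a crossover claim that is harder to reach: joint power for tier (c) is only about .22 to .40 at +.08/-.08. No participants or data are added.
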